1.1.2. Frontotemporal Lobar Degeneration, *GRN*, and *C9orf72*

Frontotemporal lobar degeneration (FTLD) can be broadly split into 3 principal pathology categories based on manifest nuclear and cytoplasmic inclusions: (1) FTLD-TDP, with neuronal and glial inclusions immunoreactive for transactive response, transactive response DNA-binding protein of 43 kD (TDP-43); (2) FTLD-tau, with tau-positive inclusions containing fibrillar, hyper-phosphorylated tau; and (3) a small number of tau-negative, TDP-43-negative cases which are immunoreactive to the fused in sarcoma protein (FTLD-FUS) (Perry 2017; Mann 2017). TDP-43 pathology is seen in most FTD cases caused by a genetic mutation and is identified in up to 50% of FTD patients overall (Ng 2015).

A family history is present in approximately 40% of FTD cases, with about 10% showing an autosomal dominant pattern of inheritance (Deleon 2018), indicating a strong genetic component. *Granulin* (*GRN*) mutations account for up to 20% of all heritable FTD cases, and 5 to 10% of all cases of FTD are caused by a loss-of-function mutation in 1 allele of *GRN* (Gass 2006; Rademakers 2012; Rohlfing 2017; Cruts 2012). Heterozygous *GRN* deficiency almost invariably leads to development of FTD, making *GRN* a causal gene for the disease (Boxer 2013a; Boxer 2013b).

GRN mutations include 77 different mutations in more than 240 unrelated families, which accounts for 16% of families worldwide carrying a neurodegenerative disease-causing mutation (Ghidoni 2012) that encodes for the secreted glycoprotein progranulin (PGRN) (Rademakers 2012). Frontotemporal dementia patients carrying this mutation have a >50% reduction in plasma and cerebrospinal fluid (CSF) levels of this secreted protein (Meeter 2016). Progranulin is associated with many cellular processes that include, but are not limited to, embryogenesis, inflammation, wound repair, neurodegeneration, and lysosome function (Chitramuthu 2017). In

the brain, PGRN promotes neurite outgrowth (Gass 2012) and enhances the survival of motor and cortical neurons (De Muynck 2013). The predominant clinical presentation of *GRN* mutation patients is bvFTD or PPA.

C9orf72 hexanucleotide repeat expansions are also a significant contributor to FTD pathology. Expansion of a non-coding hexanucleotide repeat in *C9orf72* is the most common single cause of FTD, representing approximately 25% of familial cases and 6% of sporadic FTD cases (Ng 2015). Currently, the pathophysiology of frontotemporal dementia in carriers of *C9orf72* hexanucleotide repeat expansion mutations causative of FTD is unclear but may involve haploinsufficiency of the *C9orf72* protein or abnormal dipeptide repeat proteins (data on file). The predominant clinical presentation (>80%) of *C9orf72* repeat carriers is bvFTD, with motor neuron disease (FTD-MND) or without motor neuron disease (Ng 2015).

FTD patients with *GRN* and *C9orf72* mutations exhibit a common pathology in frontotemporal degeneration associated with TDP-43 protein-related accumulation. Overlapping functional associations between *GRN* and *C9orf72* proteins include processing of TDP-43, and abnormal glial activation in patients with FTD (Ayala 2008; Zhang 2009; Mann 2017; Valdez 2017; Busch 2016; Zhang 2007; Tanaka 2013; O'Rourke 2016). Moreover, studies have suggested that TMEM106b may be a genetic modifier of both *C9orf72* and *GRN* (Gallagher 2014; van Blitterswijk 2014; Pottier 2018), suggesting that these genes may share a common pathway. Therapeutics targeted at reducing TDP-43 pathology and restoring lysosomal function may thus also slow FTD disease progression in patients with either *GRN* or *C9orf72* mutations.

1.1.3. Sortilin and AL001

Human and mouse genetic studies identified the transmembrane receptor Sortilin, encoded by the *Sortilin 1* gene, as the major negative regulator of PGRN levels in plasma and the brain (Hu 2010; Carrasquillo 2010). Sortilin binds PGRN and targets it for lysosomal degradation resulting in a reduction of extracellular PGRN. Blocking Sortilin/PGRN interactions, therefore, provides a therapeutic strategy for sustaining PGRN levels in the central nervous system (CNS) and minimizing progression of FTD-associated dementias.

AL001 is a recombinant humanized monoclonal antibody that binds specifically to Sortilin and is being studied for the treatment of carriers of *GRN* mutations causative of FTD and carriers of *C9orf72* hexanucleotide repeat expansion mutation causative of FTD.

1.2. Findings from Nonclinical and Clinical Studies of AL001

1.2.1. Nonclinical Studies

To support clinical studies, the toxicology and pharmacokinetics (PK) of AL001 were evaluated in single- and repeat-dose PK studies and Good Laboratory Practices (GLP) repeat-dose (4-week and 26-week) intravenous (IV) toxicology studies in cynomolgus monkeys. Overall, for the dose levels assessed, there were no significant toxicology findings in the nonclinical studies.

Refer to the AL001 Investigator's Brochure (IB) for additional details regarding nonclinical pharmacology, PK, and toxicology data.

1.2.2. Clinical Studies

1.2.2.1. Study AL001-1 (Completed)

Study AL001-1 was a first-in-human (FIH) Phase 1 study that assessed the safety, tolerability, PK, and PD of AL001 in healthy volunteers (HV) and carriers of *GRN* mutations causative of FTD. The study was conducted in two parts.

Part 1, Healthy Volunteers

The first part of this study evaluated the effect of single doses of AL001 ranging from 2 mg/kg to 60 mg/kg in HV to identify the safest maximum dose and explore pharmacokinetics (PK) and pharmacodynamics (PD) in plasma and cerebrospinal fluid (CSF). A total of 50 HV were enrolled: 42 participants in 5 randomized single-ascending-dose cohorts (Cohorts 1 through 5) with increasing dose levels of AL001 (or placebo) ranging from 2 mg/kg to 60 mg/kg via IV administration, plus 8 participants in the single-dose 60 mg/kg expansion cohort (Cohort 6).

Plasma PGRN Concentrations: Administration of AL001 to HV at single doses of 2 mg/kg, 6 mg/kg, 15 mg/kg, 30 mg/kg, and 60 mg/kg caused dose-dependent peripheral increases in plasma PGRN levels; the elevations of PGRN levels were sustained for a longer duration at the highest dose levels. Maximum concentrations of PGRN were measured 5 to 12 days after the infusion. At the 30 mg/kg dose, plasma PGRN concentrations remained elevated at more than twice the baseline level, from 2 days after dosing to 29 days after dosing. At the 60 mg/kg dose, plasma PGRN concentrations remained elevated at more than twice the baseline level, from 2 days after dosing to more than 29 days after dosing. The maximum percent increase in percent change from baseline was statistically significant compared to pooled placebo for each of the HV dose cohorts, and ranged from 2.29 (2 mg/kg) to 3.14-fold (60 mg/kg) over baseline. CSF samples were collected from HV in the 15 mg/kg, 30 mg/kg, and 60 mg/kg dose cohorts before dosing and approximately 30 hours (Day 2) and 12 days (Day 13) after the infusion.

CSF PGRN Concentrations: A statistically significant increase in CSF PGRN levels (compared to baseline) was seen at both post-dose time points for each of these 3 cohorts (Day 2 and Day 13). The maximum increase in CSF PGRN was observed 12 days after dosing: 1.57 times for 15 mg/kg, 1.84 times for 30 mg/kg, and 2.11 times for 60 mg/kg compared to baseline. No statistically different changes in CSF PGRN levels have been observed in subjects that received placebo. In the 60 mg/kg expansion cohort, 24 days after dosing, the PGRN level was increased 1.83-fold over baseline and 42 days after dosing the PGRN level was increased 1.23-fold over baseline. Coefficients of variation were in the range of 20% to 40% for the 30 mg/kg and 60 mg/kg cohorts over the cited sampling period.

Safety: AL001 was generally safe and well tolerated through the highest dose assessed (60 mg/kg), without dose-limiting toxicities or apparent trends in adverse events (AEs).

Part 2, Patients with Asymptomatic FTD-*GRN* or Symptomatic FTD-*GRN*

The second part of the study was conducted in two cohorts: the first cohort assessed safety, PK, and PD after a single-dose of AL001 in asymptomatic carriers of a loss-of-function *GRN* mutation causative of FTD (asymptomatic FTD-*GRN*); while the second cohort assessed safety,

PK, and PD after repetitive dosing in symptomatic FTD carriers of a loss-of-function *GRN* mutation (symptomatic FTD-*GRN*). A total of 6 asymptomatic FTD-*GRN* participants and 8 symptomatic FTD-*GRN* participants were enrolled and completed dosing in the second portion of the study. Asymptomatic FTD-*GRN* participants were administered a single IV dose of AL001 at 60 mg/kg and symptomatic FTD-*GRN* participants were administered 3 doses of IV AL001 30 mg/kg, q2w.

Plasma PGRN Concentrations: Consistent with the literature (Meeter 2016), both the asymptomatic FTD-*GRN* cohort (N = 5 who received 60 mg/kg) and the symptomatic FTD-*GRN* cohort (N = 8) had substantially lower baseline plasma PGRN concentrations than HV cohorts (1 asymptomatic participant was incorrectly dosed and is not included in the summary pharmacodynamic analyses). Mean baseline plasma PGRN concentration for the asymptomatic FTD-*GRN* cohort was 32.6 ng/mL (standard deviation [SD] of 13.6); for the symptomatic FTD-*GRN* cohort, mean baseline plasma PGRN concentration was 31.7 ng/mL (SD of 12.7). Treatment of the asymptomatic FTD-*GRN* cohort with a SD of 60 mg/kg AL001 resulted in an increase of plasma PGRN to approximately the baseline level of HV for 24 days (median concentrations of 118 to 124 ng/mL at Day 6 through Day 30 of the study). Treatment of the symptomatic FTD-*GRN* cohort with 3 doses of 30 mg/kg AL001 over a 4-week period resulted in an increase of plasma PGRN to at least 80% of the baseline level of HV for approximately 49 days, beginning 7 days after the first dose (median concentrations of 93.7 to 97.6 ng/mL at Day 8 through Day 57 of the study).

CSF PGRN Concentrations: Parallel to the results observed for plasma concentrations of PGRN, both the asymptomatic FTD-*GRN* cohort (N = 5 who received 60 mg/kg) and the symptomatic FTD-*GRN* cohort (N = 8) had substantially lower baseline PGRN concentrations in CSF than HV cohorts (mean of 1.67 ng/mL for the asymptomatic FTD-*GRN* cohort, 1.82 ng/mL for the symptomatic FTD-*GRN* cohort; approximately 55 to 58% of the HV mean of 3.1 ng/mL). Treatment of the asymptomatic FTD-*GRN* cohort with a single-dose of 60 mg/kg AL001 resulted in an increase of PGRN in CSF to 3.76 ng/mL, approximately 1.2 times the baseline level of HV, assessed 12 days after dosing. Treatment of the symptomatic FTD-*GRN* cohort with 3 doses of 30 mg/kg AL001 over a 4-week period resulted in an increase of PGRN in CSF to 3.76 ng/mL, approximately 1.2 times the baseline level of HV, assessed 28 days after the third dose of 30 mg/kg AL001 (57 days after the initial dose).

Safety: There were no deaths, no AL001-related serious adverse events (SAE)s, and no dose-limiting AEs. AEs have been predominantly mild to moderate in severity.

1.2.3. Study AL001-2 (Ongoing)

The current Phase 2 study, AL001-2, will evaluate the long-term safety profile of AL001 in heterozygous carriers of *GRN* or *C9orf72* mutations causative of FTD. The study will be conducted in two parts. During Part 1 (Treatment Period), participants will receive open-label treatment with 60 mg/kg IV AL001, administered every 4 weeks (q4w) for 96 weeks. Part 2 is an optional open-label extension (OLE) to assess long-term (up to 96 weeks extended treatment period) safety and tolerability in participants who complete the Part 1 96-week treatment period. Enrollment in this Phase 2 study was initiated in the third quarter of 2019. The first participant

was dosed on 27 September 2019. Target enrollment of 40 subjects is planned; up to 20 subjects with *GRN* mutations including participants from Study AL001-1 and up to 20 patients with *C9orf72* mutations. See [Section 1.4.3](#) for a discussion of the rationale for the dosing period.

1.3. Risk/Benefit Assessment of AL001

Refer to the IB for detailed information on safety profile of AL001.

1.3.1. Known Risks of the Drug Class

Immune Response: Monoclonal antibodies like AL001 may be associated with a potential immune response, such as hypersensitivity or hypersensitivity-like reactions, including severe anaphylactic reactions.

1.3.2. Risks of AL001

Risks Associated with AL001 Study Procedures and Assessments: The study procedures and assessments to be performed are not considered to be of great burden to patients and are not associated with high risk.

Important Identified Risks: There are no important identified risks for AL001.

Serious Adverse Drug Reactions: No serious adverse drug reactions (ADRs) have been identified in Study AL001-1 or Study AL001-2 and there are no expected serious ADRs for AL001.

Immunogenicity: Subjects treated with AL001 have developed anti-drug antibodies (ADAs). The preliminary assessment of ADAs has not identified any associations between incident ADAs with PK, PD, or clinical safety in participants receiving single-dose AL001 or three doses of AL001 administered q2w. Based on the current information from studies with AL001, the impact of immunogenicity on AL001 exposure, PD effects, and clinical safety do not appear consequential with short duration of exposure. However, the impact of ADAs continues to be assessed in ongoing AL001 clinical studies with longer-term exposure. An ADA assay for neutralizing antibodies to AL001 is under development. See the IB for more information on immunogenicity.

Adverse Events: AL001 has been generally safe and well-tolerated. There have been no deaths, no AL001-related SAEs, and no adverse events (AEs) leading to study discontinuation in the clinical trials of AL001 to date. AEs have been predominately mild to moderate in severity. Refer to the IB for a detailed summary of AEs.

Summary of Adverse Events – Study AL001-1 (completed): There were no deaths and no dose-limiting adverse events (DLAEs). There was no higher incidence of treatment emergent adverse events (TEAEs) with AL001 treatment than with placebo, and the incidence of TEAEs was similar across all AL001 dosing regimens and between the HV and FTD-*GRN* cohorts. There were no dose-related trends in TEAEs. The most frequent TEAEs were post-lumbar puncture syndrome (i.e., headache after lumbar puncture), headache, puncture site pain, anemia, lipase increased, myalgia, vomiting, and upper respiratory tract infection.

1.3.3. Potential Benefits of AL001

AL001 is being evaluated as a potential disease-modifying treatment of adults at risk for or with FTD due to a mutation in *GRN* that leads to lower levels of PGRN. AL001 is a novel recombinant human monoclonal IgG1 antibody that blocks Sortilin, decreasing the rate of PGRN clearance, and raising the concentration of PGRN. AL001 may therefore decrease the rate of neurodegeneration and clinical decline associated with FTD among patients who carry *GRN* mutations. Treatment with AL001 represents a promising therapeutic strategy, not only for FTD patients, but also for individuals who are at risk for developing FTD and while the efficacy of treatment with AL001 is still under investigation, patients with or at risk for FTD may benefit from participating in clinical trials of AL001, which are designed to evaluate a potential treatment for a disease for which there is currently no treatment or cure. All participants will receive and potentially benefit from close medical monitoring and care from qualified professionals throughout their participation in the study.

1.3.4. Benefit Risk for AL001-2 Study Participants

Frontotemporal dementia is a rare, early-onset form of dementia. Frontotemporal dementia progresses rapidly with survival after symptom onset of 3 to 14 years (Onyike and Diehl-Schmid 2013). There are currently no approved treatments for FTD (Boxer 2013a, Boxer 2013b).

Participation in Study AL001-2 offers the possibility of receiving AL001, a novel recombinant human monoclonal IgG1 antibody that blocks Sortilin, for the treatment of adults at risk for or with frontotemporal dementia due to a mutation in the *GRN* that leads to lower levels of PGRN. By blocking Sortilin, decreasing the rate of PGRN clearance and therefore raising the concentration of PGRN, AL001 may decrease the rate of neurodegeneration and clinical decline associated with FTD among patients who carry *GRN* mutations. Study participants will be randomly assigned to either AL001 or placebo.

More detailed information about the known and expected benefits and risks of AL001 may be found in the current version of the AL001 IB.

The potential benefit of AL001 to participants is described in [Section 1.3.3](#) of the protocol, and based on completed Phase 1 study, AL001-1, which demonstrated that AL001 is associated with significant and dose dependent increases in plasma and CSF PGRN in both healthy volunteers, asymptomatic and symptomatic carriers of *GRN* mutations causative of FTD. Of note, administration of AL001 to subjects with *GRN* mutations restored CSF and plasma PGRN levels to normal. In addition, by blocking Sortilin, decreasing the rate of PGRN clearance and therefore raising the concentration of extracellular, AL001 may reduce TDP-43-associated pathology and decrease the rate of neurodegeneration and clinical decline associated with FTD among patients who carry *C9orf72* mutations.

The safety profile of AL001 for participants in this study is described in [Section 1.3.2](#), with further guidance for investigators provided in the IB. Any risks to participants in AL001-2 will be minimized through a combination of screening for appropriate eligibility criteria (see [Section 4](#)), and rigorous safety monitoring to mitigate risks and careful toxicity management (see [Section 6.5](#), [Section 7](#), and IB). Adverse event and/or severe adverse event collection will occur up to 8 weeks after last dose of study treatment. Frequent safety monitoring will ensure that updated safety information is available in a timely manner and that any future changes to the benefit-risk profile of AL001 are appropriately reported and managed. An independent Data Monitoring Committee (iDMC) with the capability of reviewing unblinded data will provide additional oversight of the study supplementing the Sponsor's careful screening, diligent monitoring and management of patient safety.

Taking the available data on the investigational therapy together with the study design and conduct, AL001 is anticipated to be generally safe, well tolerated and provide pharmacological effect at the dose of 60 mg/kg being administered. Subjects, regardless of the treatment group to which they are randomly assigned, will receive close medical monitoring and care from qualified professionals throughout their participation in the study. The assessment procedures included in the clinical studies are not considered to be of great burden to patients and are not associated with high risk. Informed consent processes are intended to both (1) describe these potential benefits and potential risks from participating in the study and (2) ensure, in accordance with

local regulation, that a legally authorized representative is identified for participants who may not have legal capacity to provide consent as described in [Section 10.3](#) of the protocol.

Therefore, it is plausible to conclude that the anticipated benefits of participating in this study outweigh the potential risks or inconveniences.

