5. STUDY TREATMENTS

This is an open-label study; all participants will receive AL001 (Part 1 treatment period and Part 2 optional OLE).

Each participant who provides informed consent will be assigned a screening number that uniquely identifies the participant. It is the responsibility of the investigator to ensure each participant is eligible for the study prior to enrollment. Participants who complete Part 1 will retain their unique screening number if they participate in Part 2. Alector will maintain a central screening log and utilize an electronic data capture (EDC) and Interactive Response Technology (IRT) systems to implement enrollment, to assess current inventories of AL001, to initiate necessary resupply of drug and to document discontinuation of drug.

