5.5. Blinding

This is an open-label study where all participants will receive AL001, and doses are not concealed; blinding, therefore, is not required.

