6.5.1. Adverse Events

All AEs and SAEs must be recorded and reported, regardless of cause or relationship, that occur after the participant signs informed consent and through the Part 1/Part 2 EOS or Safety Follow-up visit, whichever is later. Any unresolved AEs and SAEs will be followed up through satisfactory clinical resolution. Additionally, SAEs considered related to study drug which occur at any time should be reported by the investigator regardless of the AE/SAE collection window. Definitions describing what is and is not considered an AE are provided in [Section 7.1](#).

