6.13. Safety Follow-up Visit

A Safety Follow-up visit will be performed 10-weeks following the last dose of AL001. The Safety Follow-up visit may be substituted by a scheduled visit if it occurs within the same window.

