7.1. Serum Pharmacokinetics Samples

Blood samples will be collected for assessment of serum concentrations of AL001. All serum PK samples should be drawn from the arm that is not used for the infusion on day of study drug administration. Specific information on PK sample collection, processing, storage, and shipment will be provided in a separate manual. Serum PK samples for AL001 will be collected at predose and at the end of infusion (within 15 minutes after the end of infusion) on weeks 1, 2, 5, 9, 13, 17, 21, 25, 29, 33, 37, 41, 45, 49, 53, 61 (3h post EOI and 24h also), 73, 85, 97, and 105 or study completion/ET for all participants.

Serum concentration and time deviation data at each study visit/timepoint will be presented in data listings by cohort (aFTD-GRN, FTD-GRN, FTD-C9orf72) at baseline in the Safety population. Serum concentration data will be summarized by study visit/timepoint and cohort at baseline for the PK analysis population using descriptive statistics: number of participants with non-missing data (n), mean, SD, CV, median, minimum, maximum, geometric mean, and geometric CV. All serum concentration values below the limit of quantification (BLQ) will be set to zero when calculating summary statistics.

Mean serum concentration versus nominal time profiles will be plotted on both linear and semilogarithmic scales for the PK analysis population by cohort at baseline. Individual serum concentration versus actual time profiles will be plotted on both linear and semilogarithmic scales for the Safety population.

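### Protocol 1.3.4 states an 8-week adverse event collection period against 10 weeks elsewhere, and the SAP 7.1 and 8.1 sampling lists and 10.1 windows are out of step with the current follow-up schedule

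*Protocol*

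**What the plan says.** **Adverse event window.** The benefit-risk section, Protocol 1.3.4, states "Adverse event and/or severe adverse event collection will occur up to 8 weeks after last dose of study treatment". Protocol 6.5.1 records all AEs and SAEs "through the Part 1/Part 2 EOS or Safety Follow-up visit, whichever is later", and 7.5 and the schedule footnotes repeat this. Section 6.13 adds "A Safety Follow-up visit will be performed 10-weeks following the last dose of AL001". The footnotes date that visit to Week 107 (±7 days) after Part 1 (Table 5) and Week 207 after Part 2 (Table 8). Both tables mark AE review at the visit itself.

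**Design wording.** Section 1.3.4 also says "Study participants will be randomly assigned to either AL001 or placebo", whereas Section 5.5 says "This is an open-label study where all participants will receive AL001, and doses are not concealed". SAP 2.2 agrees with 5.5.

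**Sampling lists.** SAP 7.1 ends its list of serum PK weeks with "73, 85, 97, and 105 or study completion/ET for all participants", and SAP 8.1 ends its plasma PGRN list the same way. The SAP's own appendices differ:
- Appendix 14.2 places Safety Follow-up at Week 107.
- Appendix 14.3 marks PK and PGRN samples at that visit.
- Appendix 14.6 marks both at OLE Weeks 121, 145, 169 and 197, at Part 2 EOS and at the Part 2 Safety Follow-up. It marks neither at Week 105 (V28).

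**Analysis windows.** SAP 10.1 assigns Days 632 to 757 to Week 97, opens Week 121 at Day 758, and assigns everything from Day 1276 to Week 197. There is no follow-up category.

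**The concern.** AE and SAE incidence leads the list of primary safety endpoints. Outside the collection period the protocol asks only for SAEs considered related to study drug. Whether a non-serious AE, or an unrelated SAE, in the last two weeks before Safety Follow-up is recorded should therefore not depend on which section is read.

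In the SAP, a programmer working from 7.1 and 8.1 would look for a Week 105 sample that is not scheduled. The lists would not mention the OLE or follow-up samples that are. Yet SAP 1.1 keeps PK and plasma PGRN endpoints for Part 2, and SAP Section 2 combines the two parts.

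The windows matter because SAP Section 12 makes PGRN the marker of target engagement, the Sortilin assay having been dropped. A PGRN value taken off drug should not be able to appear as an on-treatment value.

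**Working it through.** **Inputs.** Last Part 1 dose at Week 97, Day 673, and last Part 2 dose at Week 197, Day 1373 (Protocol Tables 5 and 8). AE collection to 8 weeks (1.3.4) or to a visit at 10 weeks, ±7 days (6.13, Table 5). Windows from SAP 10.1.

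**1. Reproduce the plan's own dates.** Study day = 7 × (week − 1) + 1.
- Week 97: 7 × 96 + 1 = 673, as tabulated.
- Week 105: 7 × 104 + 1 = 729, as tabulated.
- 10 weeks after Week 97: 673 + 70 = 743, and 7 × 106 + 1 = 743, which is Week 107 as stated.
- 10 weeks after Week 197: 1373 + 70 = 1443, which is Week 207 as stated.

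**2. Difference between the two AE periods.** 70 − 56 = 14 days. The ±7-day window for Safety Follow-up runs from Day 736 to Day 750 (9 to 11 weeks after the dose). Eight weeks is Day 729, which is 7 days before that window opens.

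**3. SAP lists against SAP appendices.**

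| Time point | SAP 7.1 and 8.1 lists | SAP Appendices 14.3 and 14.6 |
|---|---|---|
| Week 105 (V28) | listed | no PK or PGRN sample |
| Weeks 121, 145, 169, 197 | not listed | PK and PGRN |
| Safety Follow-up (Parts 1 and 2) | not listed | PK and PGRN |
| Study completion/ET | listed | PK and PGRN at EOT/EOS |

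Week 105 is 105 − 97 = 8 weeks after the last Part 1 dose. The SAP does not itself print an 8-week period.

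**4. Where follow-up samples fall in the SAP 10.1 windows.**
- After Part 1: Day 743, and the whole range 736 to 750, lies inside 632 to 757, so it is assigned to Week 97.
- After Part 2: Day 1443 is at least 1276, so it is assigned to Week 197.
- Illustration, early stop: last dose at Week 49 (Day 337) gives 337 + 70 = 407, inside 394 to 463, so it is assigned to Week 61.

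The scheduled Week 97 PGRN sample is pre-dose, 673 − 645 = 28 days after the Week 93 dose. The follow-up sample is 70 days after the last dose. Protocol 1.2.2.1 gives an indication that the effect fades with time since dosing: in healthy volunteers, CSF PGRN was 1.83-fold over baseline 24 days after a single 60 mg/kg dose and 1.23-fold at 42 days. The documents give no plasma figure at 70 days after the last dose.

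**5. What the selection rule does.** SAP 10.1 uses the nominal-visit value if there is one, and otherwise the closest unscheduled value in the window. Safety Follow-up is a scheduled visit but has no nominal row in 10.1. The rule therefore does not say whether its value is dropped, listed only, or used to fill a missing treatment visit.

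**The case against.** Section 1.3.4 is background text, and the sentence before the 8-week statement sends the reader to Sections 6.5 and 7 for safety monitoring. Every operative section agrees with the others, and the schedules mark AE review at Safety Follow-up. SAP 6.1 sets no end date for a treatment-emergent event, so the planned AE analysis is not cut at 8 weeks. This stands, and it limits the point to a contradiction in wording.

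The SAP lists describe collection and are not table shells. Sections 7.1 and 8.1 also call for summaries by time point, 10.1 already has windows for Weeks 121, 145, 169 and 197, and the Part 2 PK and PGRN endpoints are exploratory. This stands too: a reader might infer that Part 2 will have no PK or PGRN output, and the documents do not support that. It does not answer the absence of a follow-up category. The wording about study completion/ET does not supply one either, because Appendices 14.3 and 14.6 give EOT/EOS and Safety Follow-up separate rows.

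Four other readings go too far:
- That the SAP shortens AE follow-up to 8 weeks. Its Week 105 entries concern sampling only, and its Appendix 14.2 gives Week 107.
- That V28 has only vital signs. That is true of the PK/PD sub-table. The full schedule also has study drug, pregnancy test, AE review, Sheehan-STS and an optional speech assessment.
- That the reference in 1.3.4 to the iDMC reviewing unblinded data is false. In an open-label trial it is redundant.
- That the benefit-risk conclusion depends on a placebo arm. The argument in 1.3.4 rests on PGRN elevation, the Phase 1 results and monitoring. The randomisation sentences are stray text.

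**Conclusion.** The point holds as an internal inconsistency with two parts.

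First, the protocol states two collection periods for AEs, 14 days apart, and the passages must be reconciled. A reader might infer that two weeks of AE data are lost for every participant. The documents do not show that. It would require a site to follow 1.3.4 over all the operative sections, and participants who enter the OLE continue dosing and meet this gap only after their last OLE dose. Nothing here says which length is clinically right.

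Second, the SAP 7.1 and 8.1 lists do not match the SAP's own appendices: one listed week has no sample, and four OLE weeks and the Safety Follow-up are missing. Under 10.1 an off-drug PGRN value at Day 743 shares the Week 97 category and could be read as on-treatment. This assumes that the 10.1 windows, which are said to cover all PD biomarker analyses but sit in the exploratory section, also govern plasma PGRN. Those windows do not apply to serum PK, where the defect is confined to the list. The documents do not say how many participants would be affected, and no sample-size figure changes.

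**What to change.** - Protocol: reconcile 1.3.4 with 6.5.1, 6.13 and 7.5 so that a single AE and SAE collection period is stated throughout. The choice of length is the sponsor's.
- SAP 7.1 and 8.1: align the lists with Appendices 14.3 and 14.6, removing Week 105 and adding Weeks 121, 145, 169 and 197 and the Safety Follow-up.
- SAP 10.1: state that the Safety Follow-up sample is reported as its own off-drug time point, indexed to the last dose, and is not mapped to a treatment-visit window. Use the same time point for PK in 7.1.
- Editorial only: remove the randomisation and placebo sentences from 1.3.4, and correct severe to serious in the AE collection sentence.

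The cost is wording in one protocol section and three SAP sections, with no new visits, samples or data. The protocol change can go into the next amendment. The SAP changes should be made before database lock.
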